c.5. Preliminary Studies. This is a feasibility study so no preliminary data for this protocol have been collected. [name] has recently successfully developed and tested a standardized acupuncture protocol for the treatment of women with vulvodynia⁶⁵. [name], has extensive expertise in symptoms, gender, and measurement and has received substantial extramural (F31, T32, R15, R01) and intramural funding for her cardiovascular research. She has developed a validated symptom checklist for patients with acute coronary syndrome and has been funded on several studies to examine the acute and chronic symptoms of IHD⁶⁶⁻⁶⁸.

c.6. Methods

c.6.1. Sample & Setting. Sixty-nine women and men, with a confirmed diagnosis of chest pain or stable angina will be included. We will recruit women from the Chicago metropolitan area including the UIC campus community. Inclusion criteria are: provision of a verified diagnosis from a care provider, individual, ≥ 21 years of age (since IHD presenting as angina has not been reported in children), chest pain or intermittent angina symptoms (pain, pressure, or discomfort in the chest or other areas of the upper body), and medical confirmation of a diagnosis of stable angina. Exclusion criteria include pregnancy, , COPD causing pain or associated symptoms, autoimmune dysfunction, use of steroid medications, and concomitant, biofeedback, or additional acupuncture. Participants will be instructed to continue medications to treat their chest pain or angina, as well as other health conditions, as prescribed. Etiology of chest pain or angina (i.e. occlusive coronary artery disease, microvascular disease, or vasospastic ischemia) is not an inclusion criteria. Menopausal status will be adjusted for in statistical analyses.

The study will be conducted at the University of Illinois, College of Nursing (UIC CON) in clinical research exam rooms on the fourth floor. One Illinois licensed acupuncturist, [name], whose qualifications are described in the budget justification will be administering all 10 acupuncture treatments to 35 experimental participants (and up to 34 control group participants upon study completion) there. The exam rooms will also be utilized to obtain informed consent and for research data collection. The UIC CON is accessible by public transportation and has parking available nearby.

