c.6.5. Research Protocol. The research assistant (RA) will explain the nature of the study, risks and benefits, the voluntary nature of participation, and the ability to discontinue participation at any time without consequences. After informed consent is obtained, participants will be randomized to the acupuncture or attention control group via a computer-generated random numbers table. Each number (1-26) and assigned group, will be written on an index card and placed in a sealed opaque envelope. The participants will select

one envelope from a sealed box. The participant, acupuncturist, and RA cannot be blinded to group assignment. All participants will complete two measures at baseline: the McGill Pain Questionnaire and the Seattle Angina Questionnaire-7.⁶⁹ Those in the treatment group will repeat the measures following all 10 acupuncture sessions. Those in the control group will repeat measures during weeks 1-5 after their attention control sessions. All participants will complete the AHA Angina Log throughout the study (weeks 1-5). Venipuncture will be performed at baseline and study completion for all participants.

c.6.6. Acupuncture Protocol. The acupuncturist will swab each point with alcohol. Needles will be inserted and retained for 30 minutes. Each needle will be rotated 3 times to stimulate the *qi* in the meridian 10 minutes after insertion, at 20 minutes after insertion, and just prior to removal at 30 minutes. Needles will be inserted using the standards of clean needle technique established by the Council of Colleges of Acupuncture and Oriental Medicine⁷⁰ One size acupuncture needle, 0.25 diameter × 40 mm length, will be used. All acupuncture needles are sterile, disposable, and made of surgical stainless steel with stainless steel wound heads. Sessions will be repeated twice weekly (with at least 2 off days in between) for 5 weeks (10 sessions).

c.6.7. Acupuncture Point Prescription for Chest Pain or Angina. The standardized point prescription uses acupuncture points on the front of the body to enable individuals, many who are acupuncture naïve, to remain supine. This is aimed at reducing anxiety by enabling the participant to anticipate needle insertions.

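### Only 26 allocation cards are described for a planned sample of 69, and neither the order of allocation nor a baseline taken before allocation is secured

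*Combined protocol and SAP*

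**What the plan says.** **Sample size.** Section c.6.1 states: "Sixty-nine women and men, with a confirmed diagnosis of chest pain or stable angina will be included". The same section gives the arms as "35 experimental participants (and up to 34 control group participants upon study completion". Section c.6.2 instead takes 26 as the study's sample when it gives a detectable effect, and separately says 52 completers would be needed for a large effect. Section c.6.3 expects attrition of at most 10%. Section c.8 says enrolment will go on until 24 are retained.

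**Allocation.** Under c.6.5 participants are randomised "via a computer-generated random numbers table". Then: "Each number (1-26) and assigned group, will be written on an index card and placed in a sealed opaque envelope". The participant selects "one envelope from a sealed box". The section adds: "The participant, acupuncturist, and RA cannot be blinded to group assignment".

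**Order of events.** Sections c.3 and c.6.5 place randomisation directly after consent. In c.6.5 the baseline McGill Pain Questionnaire (MPQ) and Seattle Angina Questionnaire-7 (SAQ-7) are mentioned after the draw and after the statement on blinding. Table 1 has a baseline column but does not place it before or after the draw.

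**Not described anywhere.** Further cards, a second list, an order of opening, a record linking card to participant, or who prepares and holds the envelopes.

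**The concern.** Three things are at stake, in falling order of weight.

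1. **The cards run out.** Once the box is empty, staff must improvise. In an open trial, improvised allocation is where selection can enter.
2. **The draw is not tied to the list.** Because any envelope may be picked, the generated order is not the order of allocation. Without a log, a returned or swapped envelope would leave no trace in the procedure as described.
3. **Baseline may follow the reveal.** The Aim 2 pain and symptom measures are self-reported and the arms are known. Section c.9.2 adjusts the standardised mean difference for baseline differences. If a participant already knows the arm when answering the baseline questionnaires, that knowledge can shift the baseline score and pass into the adjusted effect size.

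**Working it through.** **Inputs.** Planned sample 69, arms 35 and up to 34 (c.6.1). Cards 26 (c.6.5). Sample 26 with detectable d = 1.10, and 52 completers for d = 0.80 at 80% power (c.6.2). Attrition 10% (c.6.3). Completers to retain 24 (c.8). The plan states neither alpha nor sidedness, so two-sided 0.05 is assumed.

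**Step 1: reproduce the plan's figures, to see what 26 means.**
- For d = 0.80, n per arm = 2(1.960 + 0.842)²/0.80² = 24.5, so 25 per arm and 50 in total. The exact t-test gives 25.5, so 26 per arm and 52 in total. The plan's 52 is reproduced.
- Detectable d with 13 per arm = (1.960 + 0.842) × √(2/13) = 1.10. The plan's 1.10 is reproduced under this approximation (the exact t-test gives 1.15).
- With 26 per arm the same formula gives 2.802 × √(2/26) = 0.78, which does not match.

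So in c.6.2 the 26 is the total for both arms. Reading the cards as 26 per arm finds no support there, and 52 cards would still leave 69 − 52 = 17 people without one.

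**Step 2: shortfall against the stated sample.** 35 + 34 = 69. 69 − 26 = 43, and 43/69 = 62.3%. The cards cover 26/69 = 37.7%.

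**Step 3: shortfall against the plan's other targets.**

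| Target | Randomised needed at 10% attrition | Cards described | Short by |
|---|---|---|---|
| 24 retained (c.8) | 24/0.9 = 26.7, so 27 | 26 | 1 |
| 52 completers (c.6.2) | 52/0.9 = 57.8, so 58 | 26 | 32 |
| 69 included (c.6.1) | 69 as stated | 26 | 43 |

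The first row is tight. Expected completers from 26 are 26 × 0.9 = 23.4. In whole people, two losses (2/26 = 7.7%) leave exactly 24 and a third (3/26 = 11.5%) leaves 23. The rule in c.8 would then call for a 27th participant, for whom no card exists.

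**Step 4: can the two sample sizes be derived from one another?** At the plan's own attrition, 26/0.9 = 28.9 (29) and 52/0.9 = 57.8 (58). Neither gives 69. The documents do not show which figure is current.

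**Step 5: order and traceability.** No arithmetic applies. The text supplies a generated table, numbered cards and sealed envelopes. It does not supply a rule that envelopes are opened in number order, a record of which card went to whom and when, or a requirement that baseline come before the draw.

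**The case against.** The strongest reply is that this is a sample-size inconsistency and not a faulty method of randomisation. The 26 is used coherently in c.6.2 and c.6.5 and fits the 24 in c.8, and only c.6.1 disagrees on the number to be enrolled. That stands, and it shapes the fix. It does not remove the shortfall, because step 3 shows that 26 cards leave no margin for the plan's own replacement rule.

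It is also fair that this is a feasibility pilot, that sealed opaque envelopes in a sealed box are real concealment safeguards, and that a blind draw from such a box is itself random. Departing from list order does not by itself bias allocation. What is lost is the means of checking it.

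A reader might infer more than the text supports:
- **That the research assistant watches the draw, or that concealment fails because the assistant is unblinded.** The text does not say who is present. Knowing the arm afterwards is not the same as knowing it before the draw.
- **That there is no audit trail at all.** The table and the numbered cards could be checked if kept. The missing piece is the link to participant and date.
- **That every outcome is an unblinded self-report.** The biomarkers and the Aim 1 counts of recruitment, retention and completion are not.
- **That the next arm can be guessed by counting opened cards.** This needs a balanced box of known composition, and c.6.5 states neither. It would also argue against small blocks. With n cards per arm, expected correct guesses are n + 0.5 × (4ⁿ/C(2n,n) − 1). That is 15.73 of 26 (60.5%) for n = 13, but 2.83 of 4 (70.8%) for a block of four. Nothing here calls for blocks or for stratification by sex.
- **That baseline is taken after the arm is revealed.** Sentence order suggests it, but the plan does not fix the sequence.

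**Conclusion.** The card shortfall is established and must be corrected: as written, 43 of 69 planned participants (62%) have no described allocation. The figure depends on 69 being the current sample. If 26 is current, the shortfall shrinks to a missing reserve, with one more card needed as soon as a third participant is lost. Either way the sections conflict and the procedure is incomplete.

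The untied draw order and the unfixed timing of baseline are gaps in specification, not demonstrated bias. No size can be put on them from the documents. They deserve correction with the main point because the trial is open, its Aim 2 symptom measures are self-reported, its effect size is adjusted for baseline, and the remedy is nearly free.

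**What to change.** 1. Reconcile the sample size across c.6.1, c.6.2, c.6.5 and c.8, stating the number to be randomised and the number to be retained.
2. Generate one allocation list that covers the full reconciled number plus any replacement enrolment allowed under c.8.
3. Release allocations through REDCap, which c.9 shows is already in use, or through sequentially numbered sealed opaque envelopes opened strictly in order. State who prepares and holds the list.
4. Log each card number against participant ID and date.
5. State that the baseline MPQ and SAQ-7 are completed before the allocation is revealed.

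The cost is a few hours of set-up, a short log and about a paragraph of protocol text. Visits and measures do not change.

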c.6.8. Attention Control Health Videos Protocol. Individuals randomized to the attention control group will watch health videos on broad topics not containing content that could potentially improve pain. Videos will be viewed from weeks 1-5 (5 timepoints) and will equate to the time the experimental group receives acupuncture (~10 hrs.)⁷¹. Topics include *Defeating the superbugs; Can we live forever?; Do you see what I see?; Cracking your genetic code; How smart can we get?; Vaccines, calling the shots; Can I eat that?; and Alive inside (the benefits of music)*. The videos will be shown in the College of Nursing clinical laboratory room on the 4th floor. The standardized content has an additional benefit of assuring complete fidelity to the control protocol.

c.7.1. Measures.

c.7.1.a. Demographic Data Form (Appendix A). Personal characteristics will be assessed using the demographic data form. Standard measures including age, race/ethnicity, marital status, education, income, employment, and insurance are included.

c.7.1.b. Protocol Acceptability Scale for Treating Angina with Acupuncture (Appendix B). The Satisfaction instrument is a 10-item instrument used to measure acceptability of the study processes and protocols. Items are measured on a 0 (negative response, i.e. did not like acupuncture) to 2 (positive response) scale. The protocol will be deemed to have high acceptability and have an acceptability score > 10 (80%).

c.7.1.c. McGill Pain Questionnaire (MPQ) (Appendix C). The MPQ⁷² is a valid and reliable measure of pain.. The MPQ captures pain location and pain intensity on a 0 to 10 scale, where 0 is no pain and 10 is pain as bad as it can be and least and worst pain in the past 24 hours.

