c.7.1.g. **Biomarkers of Inflammation**. Proinflammatory cytokines IL-1 β , IL-2, IL-8, and IL-18; CRP^{76,77}; and TNF α , the anti-inflammatory cytokines IL-4, and IL-10,⁷⁶ and the dual pro/anti-inflammatory IL-6⁷⁸ will be measured to determine if there is a significant change baseline to post study (5 week). Venous blood (4.5 mls) will be collected in a blue-top tube containing 3.2% sodium citrate. Samples will be processed in our clinical lab in the college. Samples will be centrifuged at room temperature for 15 minutes; plasma will be removed into 2 cryovials in 1 ml aliquots and stored in a -80°C freezer immediately. A label with study ID number, date, and time of blood draw will be placed on the cryovials prior to freezing. Samples will be batch analyzed using high-sensitivity multiplex technologies.⁷⁹ See **Table 1** for all variables, measures, and data collection time points.

c.8. Potential Problems, Alternate Plans, and Limitations based on the Sample Proposed. Rigorous research into complementary and alternative therapies has been hindered by the inability to conduct placebo-controlled trials⁸⁰. Our attention control design is a strong alternative to an intervention that cannot be blinded to participant or interventionist without potential confounding treatment effects. Recruitment is always a potential problem with clinical research and we will enlist the help of the American Heart Association Chicago Affiliate and *WomenHeart* of Cook County to identify potential participants. Attrition is also a possible problem but [name] has experienced very little attrition in prior acupuncture studies. We will continue to enroll to retain 24 participants and we will address attrition with an intention to treat analysis. Design limitations were addressed in section c.3.

Table 1. Data Collection Variables, Measures, and Time Points (Both Groups)

Variable	Measure/Analyses	Data Collection Points (Baseline) (10 tx sessions) (5 wks.)		
Aim 1				
Recruitment	Number enrolled/number invited to participate	X		X
Retention	Number retained at study completion/number recruited	X		X
Completion	Number of time points completed/12 (total)	X		X
Acceptability	Protocol Acceptability Scale for Treating Angina with Acupuncture			X
Aim 2				
Effect Size	Intra-individual effect : mean pre-scores – mean post-scores/pooled s.d. Group effect : mean differences in scores between acupuncture and attention control group.	X		X

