Demographic Data	Demographic Data tionsForm	X		
Exploratory Aim				
Biomarkers	Interleukin 1 β , 2, 6, 8, 10 & 18; CRP, TNF- α	X		X
Outcome Measures				
Pain & Symptoms	McGill Pain Questionnaire; Seattle Angina Questionnaire-7; AHA Angina Log	X	X	X
Acupuncture Sensations	MASS		X	

Note: TX is treatment. s.d. is standard deviation. AHA is American Heart Association

c.9. Statistical Analysis. [name] will supervise data management and data analysis procedures. We will address missing data by intention to treat analyses (ITT), using the full information maximum likelihood (FIML) approach, which has been shown to produce unbiased parameter estimates and standard errors when data are missing at random⁸¹⁷⁷⁷⁶⁷⁶⁷⁶⁷⁶⁷⁶⁸³. All data will be exported from RedCap and imported into SAS version 9.4 for cleaning and analysis. All variables will be screened and descriptive statistics (frequencies, means,

standard deviations) will be used to describe the sample participants. Non-normal distributions may be optimally transformed using the Box-Cox method and/or analyzed using a comparable non-parametric test.

c.9.1. Aim 1: To determine the feasibility of study processes (recruitment, retention, completion, acceptability) to inform the design and execution of a future R21 study.

Hypothesis: Acupuncture therapy will be feasible (80% recruitment, retention, completion) and acceptable to individuals with chest pain or stable angina.

For the feasibility assessments descriptive statistics will be used for describing the subject characteristics and recruitment, retention & completion. We will explore patient characteristics that predict attrition and/or poor adherence to the treatment schedule. Data collected at every session will be explored to assess change in pain ratings following a session and if this pattern is consistent over the course of treatment. We are interested in knowing if pain and other symptom relief continues to improve linearly over the 5 weeks and 10 treatments or if a plateau is reached suggesting the need for fewer treatments.

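### The acceptability pass mark pairs a score above 10 with 80%, but on a summed 0-to-20 scale 10 is 50% and 80% is 16; neither the scoring rule nor the meaning of the 80% is stated

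*Combined protocol and SAP*

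**What the plan says.** Section c.7.1.b introduces the scale: "The Satisfaction instrument is a 10-item instrument used to measure acceptability of the study processes and protocols". It gives the item coding: "Items are measured on a 0 (negative response, i.e. did not like acupuncture) to 2 (positive response) scale". It then sets the criterion: "The protocol will be deemed to have high acceptability and have an acceptability score > 10 (80", where the parenthesis closes with a percent sign. The section does not say how the ten items are combined, what the 80% is a percentage of, or whether the cut-off applies to the group mean or to each participant.

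Acceptability is one of four processes named in Aim 1 (section c.9.1): "To determine the feasibility of study processes (recruitment, retention, completion, acceptability) to inform the design and execution of a future R21 study". The hypothesis beneath it reads: "Acupuncture therapy will be feasible (80% recruitment, retention, completion) and acceptable to individuals with chest pain or stable angina". There the 80% belongs to recruitment, retention and completion, and no number is attached to being acceptable. In Table 1, recruitment, retention and completion each have a formula, while the acceptability row gives only the name of the scale. The Aim 1 analysis text is descriptive and adds no rule for the score: "For the feasibility assessments descriptive statistics will be used for describing the subject characteristics and recruitment, retention & completion". In the text available, the sentence in c.7.1.b is therefore the only acceptability cut-off.

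**The concern.** A percentage in parentheses directly after a score cut-off is naturally read as that cut-off expressed as a share of the maximum. Ten items scored 0 to 2 are naturally summed to a maximum of 20. On that reading the sentence contains two different pass marks, one at half the scale and one at four fifths of it.

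What is at stake is the Aim 1 statement on acceptability, which is meant to inform the later R21 study. If the numbers are read this way, some results earn the label of high acceptability by one figure and not by the other. If the matter stays open until scores are in hand, the pass mark can be chosen with the result known.

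**Working it through.** **Inputs, all from c.7.1.b:** 10 items; item scores 0 to 2; cut-off above 10; annotation 80%. Whole-number item scores are assumed.

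**Step 1. Try to reproduce the plan's pair of figures from the summed score.**

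- Maximum = 10 × 2 = 20.
- Cut-off as a share of the maximum = 10/20 = 50%.
- Lowest total above 10 = 11, and 11/20 = 55%.
- 80% of the maximum = 0.80 × 20 = 16.
- Working backwards, 10 is 80% of 10/0.80 = 12.5, which is not a possible maximum for ten items scored 0 to 2.

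The pair does not reproduce. A participant who answers every item at the midpoint scores 10 × 1 = 10, so one point above that already passes.

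**Step 2. Try other scorings.**

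| Scoring | Maximum | 80% of maximum | Where the cut-off of 10 falls |
|---|---|---|---|
| Sum of items | 20 | 16 | 50% of maximum |
| Item mean | 2 | 1.6 | above the maximum; cannot be met |
| Count of positive items | 10 | 8 | at the maximum; exceeding it is impossible |
| Rescaled 0 to 100 | 100 | 80 | 10% of maximum |

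None gives 10 and 80% together.

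**Step 3. Read 80% as a share of participants.** A rule that 80% of participants must score above 10 has no internal conflict. It is a different rule from 80% of the maximum, as two invented sets of scores show:

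- Everyone scores 12. The share above 10 is 100%, which passes an 80% share. The mean is 12/20 = 60% of the maximum, which fails 80% of the maximum.
- Of ten participants, seven score 20 and three score 10. The mean is (7 × 20 + 3 × 10)/10 = 17, and 17/20 = 85%, which passes 80% of the maximum. The share above 10 is 7/10 = 70%, which fails an 80% share.

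**Step 4. Size of the disputed zone if items are summed and 80% is of the maximum.**

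- Per participant: totals 11 to 15, which is 5 of the 21 possible totals, if 80% means at least 16; totals 11 to 16, which is 6 of 21, if the strict inequality also governs the 80%.
- Group mean: any mean above 10 and below 16 (including 16 under the strict inequality). The span is 16 − 10 = 6 points, or 6/20 = 30% of the range.

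These figures count possible scores. They are not probabilities, because the documents give no expected score distribution.

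**The case against.** The strongest reply is that no arithmetic error is proved. The conflict needs two assumptions that the section does not state: that items are summed, and that 80% is a percentage of the maximum. The share-of-participants reading removes it and has some support, since Aim 1 uses 80% for recruitment and retention, which Table 1 defines as proportions of people. The section heading also points to Appendix B, which is not in the text available for this review and may hold scoring instructions. The sentence is itself ungrammatical, so a word may be wrong or lost. Finally, the pilot is descriptive: if the score distribution is reported, a reader can apply either threshold afterwards.

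Much of this stands as a limit on the claim. The inconsistency is conditional, and the documents do not show which figure was intended. It does not remove the need for a correction. The share reading is not written in the sentence, which mentions no participants, and under it the individual bar is still only just above half the maximum. A scoring rule in Appendix B could settle how items combine, but it could not make 10 of 20 equal 80%. Reporting the distribution would help readers, but it would not supply a pass mark fixed in advance.

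**Conclusion.** The point holds. If the ten items are summed and 80% means percent of the maximum, the stated cut-off is inconsistent: it sits at 50% of the scale, and the score matching 80% is 16. On the item-mean and positive-count scorings it cannot be met. On the share-of-participants reading the figures are compatible, but the rule is unwritten. On each of these readings the sentence needs repair.

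The consequence is limited to the acceptability verdict in Aim 1. The documents tie no progression decision to it, and sample size, power, effect sizes and safety do not depend on it. It should still be fixed, because it is the only stated threshold for one of the four feasibility processes. Confidence is high on the arithmetic and on the missing definition; which figure the authors meant cannot be determined.

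**What to change.** Before acceptability data are read, rewrite the criterion sentence in c.7.1.b to state three things:

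1. **The scoring rule**, for example the sum of ten items with range 0 to 20.
2. **One cut-off, with its true percentage and an explicit inequality**, for example at least 16 of 20 (80%), or above 10 of 20 (more than 50%). The current text uses a strict inequality, so moving to at least is a choice that should be stated.
3. **The unit it applies to**: the mean score, each participant, or a stated share of participants, for example 80% of participants scoring above 10 of 20.

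The choice of figure rests with the sponsor. The cost is one sentence. Keeping 80% of the maximum sets a stricter pass mark; keeping a score above 10 puts a less favourable percentage beside the label of high acceptability. Nothing else in the plan has to change.

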c.6.2. Power Analysis. This feasibility pilot study is not powered to detect significant effects for improvement in symptom outcome measures. However, In order to achieve 80% power to detect a large effect size using Cohen's classification ($EF=.80$), 52 patients randomized and completing the final symptoms assessments will be needed. Based on our sample of 26 participants, we will be able to detect a Cohen's d effect size of 1.10 as statistically significant. While a large effect size is not anticipated in this pilot feasibility study, an expanded trial will be adequately powered to explore the threshold for a clinically meaningful effect.

c.6.3. Retention Strategies. We anticipate an attrition rate of no more than 10%, which means we expect a 90% retention rate for the subjects. These numbers are based on accruals and withdrawals in [name] previous 10 session acupuncture trial for which there were 36 accruals and no withdrawals. The following retention strategies will be employed: Participants will be engaged as active partners in the research by addressing possible benefits of acupuncture (experimental group) and non-pain related health education (control group) as well as the importance of their contribution to science. Data collection will be scheduled at convenient times for participants, including weekend and evening appointments. Multiple contact information (e-mail, cell phone, and home phone) will be collected to improve adherence to appointments. We also will offer \$10 per visit to cover the cost of travel.

c.6.4. Procedures. The research assistant will screen and consent eligible individuals. The potential participants will be informed that they will either be randomized to the acupuncture group (10-acupuncture session protocol, two treatments per week for five weeks) or the attention control group. Data will be collected on tablet computers before and after each session. Control group members will be offered the acupuncture protocol at study completion.

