c.9.2. Aim 2: To estimate effect sizes for pre and post intervention scores and between the acupuncture and attention control groups for pain/symptoms, functional status and QoL. We will estimate standardized mean difference effect sizes (Hedges' g) comparing the treatment and control conditions adjusting for baseline differences and the upward bias due to our small sample size. We will also compute a standardized pre-post difference for the treatment group. Effect sizes will be calculated for pain, angina symptoms reported via survey and diary, functional status, and quality of life.

c.10. Timeline. We will prepare study materials and submit an IRB application upon notice of award. Three months is allotted for IRB approval process. The study is anticipated to begin on June 1, 2016 and be completed on August 31, 2017. See Table 2 for study timeline.

Table 2. Study Timeline

Study Phase	(Jun-Aug 16)	(Sept-Nov 16)	(Dec-Feb 17)	(Mar-May 17)	(Jun-Aug 17)
Submit IRB appl.	→ → →				
Recruit/Train RA		→			
Data Collection		→ → →	→ → →	→ → →	
Data Coding/Entry			→ → →	→ → →	
Data Analysis				→ →	
R21 Preparation				→ →	→
Manuscript Prep					→ →

References

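### The biomarker aim names no between-arm comparison; its only stated question is change from baseline to week 5, although both randomised arms are sampled at both times

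*Combined protocol and SAP*

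**What the plan says.** The biomarker question appears once, in c.7.1.g (Biomarkers of Inflammation): the markers "will be measured to determine if there is a significant change baseline to post study (5 week". The sentence does not say in which arm, against what, or by which test.

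Section c.6.5 states "Venipuncture will be performed at baseline and study completion for all participants", and Table 1, which is headed as applying to both groups, marks the biomarker row at baseline and at 5 weeks. In Table 1 the biomarkers fall under an Exploratory Aim, with a list of analytes and no analysis.

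Section c.9 has a subsection for Aim 1 (c.9.1) and one for Aim 2 (c.9.2), and none for the Exploratory Aim. The baseline-adjusted Hedges' g between arms belongs to c.9.2, whose outcome list leaves biomarkers out: "Effect sizes will be calculated for pain, angina symptoms reported via survey and diary, functional status, and quality of life". The same section adds: "We will also compute a standardized pre-post difference for the treatment group". Table 1 defines its group effect as "mean differences in scores between acupuncture and attention control group", in the Aim 2 block. The general text of c.9 allows for skewed data ("Non-normal distributions may be optimally transformed using the Box-Cox method and/or analyzed using a comparable non-parametric test") but names no contrast.

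**The concern.** The stated question can be read in two ways: as a pre-post test, or as a change score to be compared between arms. The text does not choose. The pre-post reading is realistic, because c.9.2 plans a pre-post difference in the treatment group as one of its own analyses.

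The two readings answer different questions. A pre-post test asks whether a marker moved over five weeks. It attributes to acupuncture anything else that moved the marker, such as regression to the mean, medication changes or time. The attention control arm exists to account for changes of that kind. Under a pre-post test that arm goes unused for the biomarkers, and the result does not show whether acupuncture alters inflammation. The pilot is meant to inform a later study, so a shared change mistaken for an effect could be carried forward.

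**Working it through.** **The plan's own figure.** The documents give no sample size, power or effect size for biomarkers. The nearest figure is the 52 completers in c.6.2, for symptom outcomes at d = 0.80 and 80% power. A two-sided two-sample t-test at alpha 0.05 needs 25.5, so 26 per arm, or 52 in total. The figure reproduces, and it supports two-sided 0.05 as the working alpha, which the plan does not state.

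**Inputs.** Allocation is 1:1 (c.3). The stated sample sizes conflict, so several are carried:

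- 24 retained (c.8): 24/2 = 12 per arm.
- 26 (c.6.2, "Based on our sample of 26 participants"): 26/2 = 13 per arm.
- 52 completers (c.6.2): 52/2 = 26 per arm.
- 69 (c.6.1, "Sixty-nine women and men") with 10% attrition (c.6.3): 69 × 0.90 = 62.1, so 62, or 31 per arm.

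Assumed, because the documents are silent: a drift δ common to both arms of 0.1, 0.3 or 0.5 SD of change; no acupuncture effect; and a baseline-to-week-5 correlation r of 0.3, 0.5 or 0.7.

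**Step 1: test within the acupuncture arm.** The paired t statistic has n − 1 degrees of freedom and noncentrality δ√n. At n = 12 and δ = 0.3 the noncentrality is 0.3 × √12 = 1.04 and the critical value is 2.201, so p = P(|T| > 2.201) = 0.158.

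| n per arm | δ = 0.1 | δ = 0.3 | δ = 0.5 |
|---|---|---|---|
| 12 | 0.062 | 0.158 | 0.353 |
| 13 | 0.063 | 0.169 | 0.382 |
| 26 | 0.078 | 0.313 | 0.688 |
| 31 | 0.084 | 0.366 | 0.768 |

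**Step 2: test each arm separately.** Someone might test both arms and note that only acupuncture reached significance. With no treatment effect, this happens with probability p(1 − p). At δ = 0.3:

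- 12 per arm: 0.158 × 0.842 = 0.133
- 13 per arm: 0.169 × 0.831 = 0.140 (0.141 from unrounded p)
- 31 per arm: 0.366 × 0.634 = 0.232

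These are 13%, 14% and 23%, so separate tests do not repair the problem.

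**Step 3: the randomised contrast.** Regress the week-5 value on arm and baseline value. A shift common to both arms goes into the intercept and leaves the arm coefficient unchanged. In simulation (20,000 runs per setting; n = 12, 13, 31; all three drifts and correlations, 27 settings) the rejection rate was 0.046 to 0.054.

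**Step 4: precision of that contrast.** The 95% CI half-width is about t × √(2(1 − r²)/n), in SD of the marker, with 2n − 3 degrees of freedom. At n = 12 and r = 0.5 this is 2.080 × √(1.5/12) = 0.735. Simulation, which also counts chance baseline imbalance, gives:

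| n per arm | r = 0.3 | r = 0.5 | r = 0.7 |
|---|---|---|---|
| 12 | 0.82 | 0.74 | 0.61 |
| 13 | 0.78 | 0.71 | 0.59 |
| 31 | 0.49 | 0.44 | 0.36 |

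**The case against.** The strongest reply is that this is an omission, not a wrong analysis. The sentence sits among the measures, and drawing blood twice from controls makes little sense unless the arms are to be compared. Section c.9.2 also puts the between-arm effect size first and the pre-post difference second. It is therefore fair to say that the authors may well intend a comparison. But no passage commits them to one, and the point made here is that the contrast is unspecified, not that it is ruled out.

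The drift sizes are assumed, and at 0.1 SD the within-arm rate is only 6 to 8%. That is true, and the rates are illustrative. The argument does not depend on them: a single-arm change cannot be attributed to the treatment at any drift size.

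The near-5% rate is per marker. If nine markers were tested independently at 0.05, the chance of at least one false positive would be 1 − 0.95⁹ = 37% even with the right contrast. This stands, and it is a reason to report estimates with intervals instead of verdicts of significance.

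A between-arm change score or a rank-based comparison would also use the control arm. That is correct. Naming a between-arm contrast is the essential step; baseline adjustment is preferred for its precision and because Aim 2 already uses it.

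Finally, the aim is exploratory in a feasibility pilot that is not powered for symptom effects. This limits the weight of the point but does not remove it, since the plan itself asks about significance.

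**Conclusion.** The concern holds. The plan states a biomarker question about change over time, gives no analysis for the exploratory aim, and confines its written between-arm methods to other outcomes, although the samples for the randomised comparison will exist.

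If the question is answered by a pre-post test and a shared drift of 0.3 SD is present, a spurious acupuncture finding is expected 16%, 17%, 31% or 37% of the time per marker at 12, 13, 26 or 31 per arm, instead of 5%. Over drifts of 0.1 to 0.5 SD and all four sample sizes, the range is 6 to 77%. These rates assume no acupuncture effect, two-sided 0.05, normally distributed changes and the same drift in both arms.

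The contrast should be fixed before the data are analysed. Aims 1 and 2 are unaffected.

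**What to change.** Add one sentence to c.7.1.g and a short exploratory-aim paragraph to c.9, for example: *For each marker, the week-5 value will be compared between the randomised arms, adjusted for the baseline value and transformed as section c.9 allows, and reported as an exploratory estimate with 95% CI. Within-arm change will be descriptive only.*

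While editing, reconcile the marker list: c.7.1.g names nine markers and Table 1 eight, with IL-4 missing from the table. This is a separate, minor point.

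The cost is wording only, with the same samples and assays. The downside is fewer nominally significant results and wide intervals: if the baseline-to-week-5 correlation is 0.5, about ±0.74, ±0.71 and ±0.44 SD of the marker at 12, 13 and 31 per arm.
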